2. OBJECTIVES

Primary:

- To evaluate the effects of etrasimod on esophageal eosinophilia in adult subjects with active EoE
- To evaluate the dose-response relationship of 2 doses of etrasimod versus placebo in adult subjects with active EoE
- To select an etrasimod dose based on efficacy and safety for continued development

Secondary:

- To evaluate the effect of etrasimod on dysphagia symptoms in adult subjects with active EoE

CCI [REDACTED]

- [REDACTED]
- [REDACTED]
- [REDACTED]
- [REDACTED]

3. STUDY DESIGN

3.1. Overall Design

This Phase 2 randomized, double-blind, multi-center study will evaluate the efficacy, safety, and PK of etrasimod compared with placebo for 24 weeks in adults with active EoE.

The study will consist of a Screening Period of up to 35 days, 24 weeks of double-blind treatment (Double-Blind Treatment Period), 28 weeks of active extended treatment (Extension Treatment Period), and 4 weeks of follow-up (Safety Follow-Up Period) for a total study duration of up to 61 weeks.

Eligible subjects will be randomized in a double-blinded fashion (3:3:2 ratio) to etrasimod 1 mg, etrasimod 2 mg, or matching placebo once daily. Randomization will be stratified by baseline history of esophageal dilation (yes/no) and concurrent PPI therapy (yes/no).

[figure not shown]
All subjects who complete the Double-Blind Treatment Period and meet eligibility criteria for the Extension Treatment Period may enter the Extension Treatment Period.

Subjects who were in etrasimod 1 mg or etrasimod 2 mg groups in the Double-Blind Treatment Period will continue the same etrasimod dose in the Extension Treatment Period. Subjects who were in the placebo group during the Double-Blind Treatment Period will be re-randomized (1:1 ratio) to etrasimod 1 mg or etrasimod 2 mg at entry into the Extension Treatment Period.

Subjects will have follow-up visits at 2 and 4 weeks after the last dose of study treatment after Week 52 or the Early Termination (ET) Visit.

A study design schematic is shown in [Figure 1](#).

Figure 1: Study Design

*Esophagogastroduodenoscopy
 EoE, eosinophilic esophagitis; ETR, etrasimod; F/U, follow-up; PBO, placebo.
 Numbers preceded by colons represent the randomization ratio.

3.2. Discussion and Scientific Rationale for Study Design

This Phase 2, randomized, double-blind study is designed to evaluate the safety and efficacy of etrasimod (1 mg and 2 mg) versus placebo for 24 weeks for the treatment of adult subjects with active EoE.

As previously described, EoE is a chronic, immune/antigen mediated disorder characterized histologically by esophageal inflammation with intraepithelial eosinophils and clinically by symptoms of esophageal dysfunction in adult patients (eg, dysphagia or food impaction). Therefore, to confirm eligibility, all subjects will undergo esophagogastroduodenoscopy (EGD) with biopsy and record their EoE symptoms during the Screening period. The target study population will comprise adult subjects with histologically active (ie, esophageal peak eosinophil count [PEC] ≥ 15 eosinophils [eos]/hpf) and sufficiently symptomatic EoE (ie, average of ≥ 2 episodes of dysphagia per week over 2 weeks). Treatment options for EoE include medications, dietary elimination, and esophageal dilation [46]. From a clinical standpoint, the goal of treatment is to decrease or eliminate symptoms, improve or normalize the endoscopic appearance, and decrease or resolve the disease.

Treatment assignment will be blinded to minimize evaluation and reporting biases. Due to limited EoE treatment options, etrasimod will be compared with placebo. This will permit accurate characterization of the effects of investigational etrasimod relative to the placebo effect (ie, background effect related to fluctuations in dysphagia symptom, the natural course of EoE disease, regression to the mean, or response bias due to the subject's reporting of subjective symptoms).

The endpoints of treatment for EoE include improvement of esophageal eosinophilic inflammation and clinical symptoms [47]. Therefore, several histologic primary and secondary efficacy endpoints will be used to characterize the effect of etrasimod on EoE including change (percent and absolute) in esophageal PEC and histologic response as defined by an esophageal PEC of < 15 or ≤ 6 eos/hpf. Eosinophil density is an objective, quantifiable, and highly reproducible measure that is also intrinsic to the disease definition. A symptom-based secondary efficacy endpoint (ie, change in dysphagia frequency and/or severity) will be assessed using the Dysphagia Symptom Questionnaire (DSQ), a validated and qualified patient-reported outcome

measure that has been successfully used in clinical studies investigating the efficacy and safety of novel treatments for EoE.

The primary efficacy endpoint is the percent change from baseline in esophageal PEC at Week 16. The treatment effects of 2 etrasimod doses on the reduction of esophageal tissue eosinophils will be characterized. The secondary endpoints include measures of histologic, endoscopic, and symptomatic improvement for further elucidation of the effects of etrasimod on EoE disease activities.

These primary and secondary endpoints will be assessed at Week 16, and treatment will be continued in the Double-Blind Treatment Period until Week 24. The Week 16 timepoint was selected for primary and secondary efficacy assessments based on meaningful clinical and endoscopic improvements observed in UC patients following treatment with etrasimod. Data from Phase 2 studies APD334-003 and APD334-005 in adult subjects with moderately to severely active UC demonstrated that treatment with etrasimod 2 mg once daily for up to 46 weeks (n = 31) resulted in maximal improvements in the 2 cardinal symptoms of active UC, rectal bleeding and stool frequency, by Week 16, which were sustained through Week 46 [38,39]. Although there are notable differences between EoE and UC, both are IMIDs of the gastrointestinal (GI) tract. Based on etrasimod's mechanism of action and extrapolation on the time from etrasimod treatment initiation to observed clinical effects in patients with active UC, it is hypothesized that 16 weeks of etrasimod treatment will provide sufficient time to elicit the clinical effects of etrasimod in the treatment of patients with active EoE. Study treatment will be administered over 24 weeks in a double-blinded fashion and evaluation of histologic and patient-reported outcomes will occur at Weeks 16 and 24. Ultimately, a comparison of treatment effects observed at Week 16 compared to Week 24 will be performed to confirm that Week 16 is the timepoint at which the maximal treatment effects of etrasimod are observed in subjects with active EoE.

Subjects who complete the Week 24 visit will be eligible to enter the Extension Treatment Period, where etrasimod treatment will continue for up to an additional 28 weeks. In the Extension Treatment Period, subjects treated with placebo in the Double-Blind Treatment Period will have the opportunity to receive etrasimod, and subjects who tolerated etrasimod during the Double-Blind Treatment Period may continue etrasimod therapy. The maintenance or durability of treatment effects and longer-term safety profile of etrasimod will be characterized in the subset of subjects who continue etrasimod therapy over 52 weeks. Thus, the use of an Extension Treatment Period in this study provides study subjects with ongoing access to study treatment and the opportunity to evaluate the longer-term efficacy and safety profile of etrasimod.

Finally, off-treatment safety data will be collected at 2 and 4 weeks after the last dose of study treatment is administered.

3.3. Rationale for Dose Selection

Etrasimod doses selected for evaluation in the proposed study is based on pharmacodynamic (PD) and safety data from single- and multiple-ascending dose studies conducted in healthy adult subjects, Studies APD334-001 and APD334-002, respectively, and on safety, clinical efficacy, and PD data from a Phase 2 parent Study APD334-003 and extension Study APD334-005 in adult subjects with active UC.

Study APD334-001 evaluated single doses of etrasimod 0.1, 0.35, 1, 3, and 5 mg. Dose-limiting treatment-emergent adverse events (TEAEs) of transient, asymptomatic first- or second-degree AV block, both with and without HR decrease, were observed in 3 subjects treated with 5 mg dose. No adverse events (AEs) of bradycardia or AV block were reported at doses < 5 mg. Thus, the 5 mg dose was discontinued in subsequent clinical studies. In Study APD334-002, etrasimod doses of 0.7, 1.35, and 2 mg were administered once daily for 21 days. Additionally, several dose escalation paradigms were evaluated in some subjects; these subjects received either 0.35 or 0.5 mg for 7 days followed by 2 or 3 mg for 14 days, respectively. PD data from single- and multiple-ascending dose studies demonstrated a dose-dependent decrease in the peripheral lymphocyte count. Overall, etrasimod doses 0.35 to 3 mg were well-tolerated for up to 21 days.

Similarly, in Phase 2 Study APD334-003, a dose-dependent reduction in peripheral lymphocyte counts were observed as early as Week 1 in adult subjects with active UC treated with etrasimod 1 mg or 2 mg, and lymphocyte counts stabilized at Week 4. Dose-dependent symptomatic and endoscopic improvements (ie, the Modified Mayo Score) were also observed; however, only favorable clinical effects of etrasimod 2 mg (and not 1 mg) demonstrated a statistically significant difference compared with placebo. The efficacy and safety profile of etrasimod 2 mg was characterized over 46 weeks across the originating Study APD334-003 and extension Study APD334-005. In the subset of subjects exposed to etrasimod 2 mg for up to 46 weeks, no clinically significant safety concerns were identified.

In summary, the PD and favorable longer-term safety profile of etrasimod 2 mg in adults with moderately to severely active UC suggest that it is safe to evaluate doses of etrasimod up to 2 mg as a chronic therapy in adult subjects with active EoE. It is hypothesized that by evaluating etrasimod 1 mg and 2 mg, an efficacious and safe dose for the treatment of active EoE will be identified for continued development.

3.4. End of Study

A subject is considered to have completed the study if he/she has completed all phases of the study, including the last study visit (ie, 4-Week Safety Follow-Up Visit). The end of the study is defined as the date of the last study visit of the last subject in the study globally.

4. STUDY POPULATION

4.1. Inclusion Criteria

Subjects must meet ALL the following inclusion criteria to be eligible for enrollment into the study.

1. Men or women between 18 to 65 years of age at the time of informed consent (IC)
2. Provide signed IC and willing to comply with all protocol-specified assessments and procedures
3. Have an EoE diagnosis prior to screening and histologically active disease with an esophageal PEC of ≥ 15 eos/hpf (~ 60 eos/mm²) from any level (proximal, mid, or distal) of the esophagus at the Screening EGD.
4. Have dysphagia, defined as solid food going down slowly or getting stuck in the throat with an average frequency of ≥ 2 episodes per week over 2 weeks (as documented using the DSQ during the Screening period)

4.2. Exclusion Criteria

Subjects will be excluded from study if they meet any of the following exclusion criteria.

Note: A confirmed result means there have been 2 consecutive assessments showing consistent findings meeting exclusionary values. For criteria requiring confirmed results, the 2nd assessment is needed only if the first assessment result was exclusionary.

Exclusion criteria related to medications, therapies, or GI and eosinophilic disease

1. History of any of the following non-EoE conditions or procedures that may interfere with the evaluation of or affect the histologic, endoscopic, or symptom endpoints of the study:
 - a. Conditions that substantially contribute to esophageal eosinophilia (eg, eosinophilic gastritis or enteritis [ie, eosinophilic duodenitis or colitis] with esophageal involvement, achalasia, hypereosinophilic syndrome, CD with esophageal involvement, esophageal infection [fungal, viral], eosinophilic granulomatosis with polyangiitis (formerly known as Churg-Strauss Syndrome), pemphigus with esophageal involvement, pill esophagitis, graft versus host disease, Mendelian disorders [eg, Marfan syndrome Type II, hyper-IgE syndrome, phosphatase and tensin homolog (PTEN) hamartoma tumor syndrome, Netherton syndrome, severe atopy metabolic wasting (SAM) syndrome])
 - b. Conditions that interfere with the evaluation of the esophagus (eg, esophageal varices with risk of spontaneous bleed, high-grade esophageal stenosis where an 8- to 10-mm endoscope could not pass through the stricture without dilation at the time of Screening EGD)
 - c. Conditions or procedures that substantially contribute to dysphagia (eg, histologically active Barrett's esophagitis, active erosive esophagitis Los Angeles Grade B or above, significant hiatal hernia [≥ 4 cm], esophageal resection)
2. Undergone dilation of an esophageal stricture within 12 weeks prior to Screening EGD.
3. Use of corticosteroids for the treatment of EoE within 8 weeks prior to Screening EGD.
4. Discontinue, initiate, or change dosing (dosage/frequency) of the following therapies for EoE within 8 weeks prior to Screening EGD. Subjects on any of the following therapy need to stay on a stable regimen during study participation:
 - a. Elemental diet
 - b. EoE food trigger elimination diet
 - c. PPI therapy
5. Used any immunotherapy/desensitization including oral immunotherapy (OIT) or sublingual immunotherapy (SLIT) within 12 months prior to the Screening EGD
Note: Stable (ie, ≥ 6 months prior to the Screening EGD) subcutaneous immunotherapy (SCIT) is permitted. Subjects on SCIT need to stay on a stable treatment during study participation.
6. Used any of the following immunomodulatory therapies within the timeframes prior to Baseline as indicated in [Table 1](#). The Medical Monitor should be consulted with any questions related to prior use of unlisted immunomodulatory therapies.

Table 1: Required Washout Period of Immunomodulatory Therapies

Time Frame	Therapies
Within 2 weeks	Antimetabolites (eg, AZA, 6-MP, MTX, 6-TG), calcineurin inhibitors (eg, cyclosporine, tacrolimus), MMF
Within 12 weeks (or 5 half-lives if shorter)	Anti-IL-5 antibodies (eg, mepolizumab, reslizumab, benralizumab), anti-IL-4/13 antibodies (eg, dupilumab), anti-IgE antibodies (eg, omalizumab), TNF α inhibitors (eg, infliximab), JAK inhibitors (eg, tofacitinib, oclacitinib)
Within 24 weeks	Anti-CD20 antibodies (eg, rituximab, ocrelizumab), anti-CD52 antibodies (eg, alemtuzumab), other cell-depleting therapies (eg, bone marrow transplantation, total body irradiation)
Any time prior to Baseline	Sphingosine 1-phosphate receptor modulators (eg, fingolimod, siponimod, ozanimod), natalizumab

AZA, azacytidine; IgE, immunoglobulin E; IL-4/13, interleukin-4/13; IL-5, interleukin-5; JAK, Janus kinase; 6-MP, 6-mercaptopurine; MMF, mycophenolate mofetil; MTX, methotrexate; 6-TG, 6-thioguanine; TNF α , tumor necrosis factor alpha

7. Use of moderate or strong inducers or inhibitors that inhibit or induce at least 2 of the following: cytochrome P450 (CYP) 2C8, CYP2C9, and CYP3A4 (eg, fluconazole, rifampin, enzalutamide) (Section 6.7.3) within 4 weeks prior to Baseline
8. Use of any investigational agent or device within 12 weeks prior Baseline
9. Have a known hypersensitivity to etrasimod or any of the excipients.

Exclusion criteria related to other medical history

10. Have any of the following conditions or risk factors:
 - a. Primary or secondary immunodeficiency syndromes (eg, hereditary immunodeficiency syndrome, acquired immunodeficiency syndrome)
 - b. History of organ transplant (except corneal transplant)
 - c. History of an opportunistic infection (eg, pneumocystis jirovecii pneumonia, cryptococcal meningitis, progressive multifocal leukoencephalopathy [PML])
 - d. History of disseminated herpes simplex or disseminated herpes zoster
 - e. Test positive for human immunodeficiency virus (HIV [positive HIV antibody]), hepatitis B virus (positive hepatitis B surface antigen [HBsAg]), or active hepatitis C (HCV [positive hepatitis C antibody with detectable HCV RNA]) at Screening

Note: If the Investigator suspects false positive hepatitis serology results, such as an antibody pattern indicating acute hepatitis infection, but no corresponding elevated liver enzymes and no signs or symptoms of liver disease, an infectious disease expert may be consulted. If the infectious disease expert finds no evidence of acute or chronic hepatitis infection and considers the serology results false positive and not clinically relevant, the Investigator may document (in source data and in the electronic case report form [eCRF]) that the serology results are considered false positive and may randomize the subject.

11. Have a serious infection that requires hospitalization or treatment with intravenous (IV) medications within 4 weeks prior to Baseline
12. Received a live-attenuated virus vaccine (except for recommended and age-appropriate influenza, measles/mumps/rubella, or varicella vaccine) within 4 weeks prior to Baseline
13. History of malignancy of any organ system (other than localized squamous cell or basal cell carcinoma of the skin that have been excised or resolved), treated or untreated, within the past 5 years regardless of whether there is evidence of local recurrence or metastases
14. Have active epilepsy
15. Have a history of cirrhosis
16. Have any of the following conditions or receiving treatments that may affect cardiovascular function:
 - a. Myocardial infarction, unstable angina, stroke/transient ischemic attack, decompensated heart failure requiring hospitalization or Class III/IV heart failure within 8 weeks prior to Baseline
 - b. Second-degree or third-degree AV block, sick sinus syndrome without a functional pacemaker, or periods of asystole for > 3 seconds without an implanted cardiac pacemaker
 - c. Recurrent symptomatic bradycardia or recurrent cardiogenic syncope
 - d. Confirmed Screening and Day 1 baseline vital signs (taken in the sitting position) with a HR < 50 bpm OR systolic blood pressure (BP) < 90 mm Hg OR diastolic BP < 55 mm Hg.
 - e. Confirmed Screening and Day 1 baseline ECG with PR interval \geq 200 ms or Friderica's corrected QT interval (QTcF) \geq 450 ms in males or \geq 470 ms in females.
 - f. Receiving Class Ia or Class III anti-arrhythmic drugs
 - g. Start, stop, or change dosage of Class Ib, II, or IV anti-arrhythmic drugs within 1 week prior to Baseline
17. Have active diabetic retinopathy, uveitis, retinitis pigmentosum, macular edema, or had an intraocular surgery within 12 months prior to Baseline. Refer to [Appendix 11](#) for modification in the event that coronavirus disease 2019 (COVID-19) or similar public health emergency (PHE)-related restrictions limit the capacity to perform non-essential ophthalmoscopy with OCT.
18. Have a confirmed forced expiratory volume at 1 second (FEV₁) or forced vital capacity (FVC) of < 70% predicted (prior to the administration of a short-acting bronchodilator) on Screening PFTs. Refer to [Appendix 11](#) for modification in the event that COVID-19 or similar PHE-related restrictions limit the capacity to perform non-essential PFTs.

Exclusion criteria related to test or laboratory results (performed by central laboratory)

19. Have confirmed absolute lymphocyte count (ALC) < 0.8×10^9 cells/L at Screening
20. Have confirmed aspartate aminotransferase (AST) or alanine aminotransferase (ALT) > 2 \times upper limit of normal (ULN) and total bilirubin > 1.5 \times ULN (unless consistent with a history of Gilbert's Syndrome) at Screening

21. Have confirmed moderate or severe renal impairment (estimated glomerular filtration rate [eGFR] < 60 mL/min/m²)

General exclusionary criteria

22. Lactating female who is breastfeeding
23. Females who are pregnant, evidenced by a positive serum beta-human chorionic gonadotropin (β -hCG) pregnancy test at Screening and/or urine dipstick pregnancy test at Day 1, or females who do not meet criterion a or agree with criterion b below, or males who do not agree with criterion c below
- a. A female who is not of child-bearing potential must meet 1 of the following:
- Postmenopausal, defined as no menses for 12 months without an alternative medical cause and confirmed by follicle-stimulating hormone (FSH) within postmenopausal range according to local standards
 - Had permanent sterilization procedure, such as hysterectomy, bilateral salpingectomy, or bilateral oophorectomy
- b. A female who is of child-bearing potential must agree to using a highly effective contraception method during treatment and for 4 weeks following treatment that can achieve a failure rate of less than 1% per year when used consistently and correctly. The following are considered highly effective birth control methods: Combined (estrogen and progestogen containing) hormonal contraception associated with inhibition of ovulation, which may be oral, intravaginal, or transdermal; progestogen-only hormonal contraception associated with inhibition of ovulation, which may be oral, injected, or implanted; intrauterine device (IUD); intrauterine hormone-releasing system; bilateral tubal occlusion; vasectomized partner; sexual abstinence (complete sexual abstinence defined as refraining from heterosexual intercourse for the entire period of risk associated with study treatments). The reliability of sexual abstinence needs to be evaluated in relation to the duration of the clinical study and the preferred and usual lifestyle of the subject. Periodic abstinence (eg, calendar, symptothermal, or post-ovulation methods) is not acceptable
- c. A male with pregnant or non-pregnant woman of child-bearing potential (WOCBP) partner must agree to use condoms during treatment and for 4 weeks following the last dose of study treatment
24. Any acute illness or medical condition including cognitive impairment and alcohol/drug abuse/dependence, or signs/symptoms suspicious for a serious disease that, in the Investigator's opinion, could put the subject at increased risk for safety event(s), confound interpretation of study results, or interfere with the subject's ability to comply with protocol-specified procedures or assessments.

Testing positive for COVID-19 is NOT exclusionary on its own if other exclusion criteria (#11 or #24) are not met. If a subject screen fails due to COVID-19, the subject may be re-screened for the study when their COVID-19 symptoms have improved or resolved but no sooner than 10 days after the first date of COVID-19 symptom onset. Subjects who are asymptomatic after COVID-19 recovery are not required to show a negative COVID-19 viral or serology test in order to qualify for re-screening.

For subjects who have not received the COVID-19 vaccine, it is recommended that COVID-19 vaccination is completed 14 days prior to randomization.

If a subject fails ≥ 1 screening laboratory criteria, the assessment(s) may be repeated once at the discretion of the Investigator, and the subject may be enrolled if criteria are then met, provided the assessments are completed within the Screening Period. Any laboratory assessments that are repeated beyond 1 time will need to be discussed with the Medical Monitor before proceeding.

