To protect vulnerable subjects, those with certain cardiac risks or pre-existing cardiac conditions (eg, recent myocardial infarction, cardiac conduction delay, recurrent symptomatic bradycardia or syncope) will be excluded from the study. Vital signs will be monitored closely during the study, and direct observation will be performed after the subject receives the first dose of etrasimod in each treatment period (at Day 1 [Double-Blind Treatment Period] and Week 24 [Extension Treatment Period]) or at treatment re-initiation after a defined period of treatment interruption (refer to Section 10.6.7.4 for additional information on Day 1 monitoring).

As additional safety measures, subjects with elevated liver enzymes, abnormal pulmonary function or pulmonary disease requiring hospitalization, and active retinopathy or macular edema will be excluded from the study.

Further description of identified risks, any potential risks, and the Reference Safety Information for etrasimod are provided in the current edition of the IB.

The safety profile of etrasimod coupled with a potent effect on the lymphocyte count demonstrate that etrasimod may be an effective oral treatment option for IMIDs such as EoE. Based on the favorable clinical safety and efficacy data that has been generated from etrasimod studies in healthy adults and subjects with UC, the precautions outlined above, and the current lack of safe and effective long-term oral medications for the treatment of EoE, the benefit/risk assessment justifies the further clinical development of etrasimod in subjects with EoE and the current Phase 2 study multi-center, randomized, double-blind, placebo-controlled study.

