9.3. Double-Blind Treatment Period

9.3.1. Day 1 Pre-Randomization and Predose

The day of administration of the first dose is defined as Day 1.

The following procedures/assessments must be performed and assessed again on Day 1 to confirm eligibility before randomization:

- HR and BP, followed by 12-lead ECG
- Pregnancy test for all WOCBP

If the subject remains eligible based on HR, BP, and 12-lead ECG parameters, and has a negative pregnancy test result (WOCBP only), then blood samples for laboratory and PK assessments will be collected, after the 12-lead ECG assessment is completed.

Subjects will also complete selected questionnaires to assess baseline status.

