10.6.7. Safety Monitoring Guidance

10.6.7.1. Drug-Induced Liver Injury

There is no published consensus on exactly when to stop a drug in the face of laboratory abnormalities and the decision may be affected by the clinical status of the patient and many other factors. The following can be considered a basic guide. When there is no alternative etiology for persistently elevated liver enzymes, discontinuation of study treatment should be considered, consistent with the United States FDA guidance [49], if:

- ALT or AST $> 8 \times$ ULN
- ALT or AST $> 5 \times$ ULN for more than 2 weeks
- ALT or AST $> 3 \times$ ULN **and** (total bilirubin $> 2 \times$ ULN **or** INR > 1.5)
- ALT or AST $> 3 \times$ ULN with the appearance of fatigue, nausea, vomiting, right upper quadrant pain or tenderness, fever, rash, and/or eosinophilia ($> 5\%$)

See [Appendix 12](#) for suggested actions and follow-up assessments in the event of potential DILI. Information on the grading and management of laboratory abnormalities according to assessed severity is provided in [Appendix 8](#) and [Appendix 9](#).

10.6.7.2. Guidance on Management of Lymphocyte, Neutrophil, and White Blood Cell Counts, and Monitoring for Infections

Etrasimod prevents lymphocyte egress from lymphoid tissues, resulting in a reduction in peripheral lymphocyte count and lymphocyte availability for recruitment to sites of inflammation. Site staff including investigators will be blinded to the WBC count, WBC differential (percentage and absolute number), and the TBNK panel cell count while subjects are on study treatment. During this time, WBC count, WBC differential, and the TBNK panel results will be assessed by an independent Medical Monitor (not involved in any other aspects of study conduct or data analysis) and will direct Investigators on specific actions to take. Blinded values may be released to treating physicians and Investigators as deemed medically necessary to monitor the risk of infection and/or aid in diagnostic work-up as clinically indicated, and/or as a tool to assess the effectiveness of therapeutic interventions for an infection.

ALC

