 - ^g Safety 12-lead ECGs will be performed with the subject in the supine position prior to blood sample collection and after vital signs are measured at Screening and prior to randomization on Week 0/Day 1 (Baseline), and 4 hours (± 15 minutes) after dosing on Week 0/Day 1. At the Week 24 visit, vital signs should be measured first, followed by ECGs, predose PK sample collection, study drug dosing at the study site, and first-dose cardiac monitoring for subjects continuing in the Extension Treatment Period.
 - ^h Complete physical examination (including assessments of the skin, head, eyes, ears, nose, throat, thyroid, lungs, heart, abdomen, back, lymph nodes, extremities, body weight, and height [height collected at Week 0/Day 1 Visit only]) should be performed at Week 0/Day 1 and the ET visit.
 - ⁱ PFTs include FEV₁ and FVC measurements. Where locally available, DLCO measurements will also be performed (sites where DLCO is not available should consult the Sponsor or Sponsor's delegate). If Week 24 or ET result is abnormal, then testing should be repeated as soon as able. Post-screening PFTs may be performed within 7 days of the study visit. Details regarding additional PFTs are provided in Section 10.6.5.
 - ^j Scheduled non-screening ophthalmoscopy with OCT may be performed within 7 days of the study visit. Screening ophthalmoscopy with OCT is to be conducted with subjects' pupils dilated (Section 10.6.6).
 - ^k Only for women of child-bearing potential. Serum β -hCG test required at screening. On Day 1, urine pregnancy test must be performed and negative test result verified prior to dosing. Monthly urine pregnancy test either at home or at the study site at all other visits. Visual inspection of the test result via videoconferencing for virtual assessment is recommended. If at any point there is a positive urine β -hCG test, the subject will have study treatment interrupted and a serum sample submitted to the central laboratory for β -hCG testing (Section 10.6.9).
 - ^l Clinical laboratory tests will include serum chemistry, CBC with differentials, and coagulation. Screening samples should be obtained, and results must be available and reviewed prior to the first dose of study treatment. On other study visits, samples should be obtained prior to the daily dosing. Refer to Section 10.6.4.

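### Exclusion 20 requires raised bilirubin as well as raised AST or ALT, so no objective criterion bars isolated AST/ALT elevation and the precaution named in Section 1.2 is not delivered

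*Protocol*

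**What the plan says.** **Exclusion 20 (Protocol 4.2).** A subject is excluded for a confirmed AST or ALT above 2 times the "upper limit of normal (ULN) and total bilirubin > 1.5" times ULN at Screening. An exception for a history of Gilbert's Syndrome is attached to the bilirubin limit.

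**Section 1.2.** Among the additional safety measures, it says that "subjects with elevated liver enzymes, abnormal pulmonary function or pulmonary disease requiring hospitalization, and active retinopathy or macular edema will be excluded". Its closing benefit-risk statement rests in part on "the precautions outlined above, and the current lack of safe and effective long-term oral medications".

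**Section 10.6.7.1.** For on-study management: "When there is no alternative etiology for persistently elevated liver enzymes, discontinuation of study treatment should be considered". Two of the levels listed there need neither a second laboratory abnormality nor symptoms: ALT or AST > 8 × ULN, and > 5 × "ULN for more than 2 weeks".

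**Other liver-related entry criteria in 4.2.** Exclusion 10e is viral serology. Exclusion 15 is history of cirrhosis. Exclusion 24 covers an illness or condition that, in the Investigator's "opinion, could put the subject at increased risk for safety event(s), confound interpretation of study results", or interfere with compliance.

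**Checks before dosing.** Table 7, footnote l: "Screening samples should be obtained, and results must be available and reviewed prior to the first dose of study treatment". The Day 1 step in Section 9.3.1 reads "If the subject remains eligible based on HR, BP, and 12-lead ECG parameters", plus a pregnancy test. Blood for laboratory tests is drawn after that step.

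**The concern.** Section 1.2 tells ethics committees and investigators that raised liver enzymes keep a subject out, and it counts that among the precautions justifying the trial. The operative rule keeps such a subject out only if bilirubin is raised as well. A site that follows Exclusion 20 literally can dose someone with a confirmed, isolated and possibly large AST/ALT elevation. Liver injury is a listed event of special interest for etrasimod (Section 10.6.8.1.4). What is at stake is subject safety at entry and uniform practice across sites; no error rate, power or estimand is affected.

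**Working it through.** The plan states no figure to reproduce. The check is a logical reading of the rule and a search for any other limit.

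**1. The rule as written.** Exclude if [(AST > 2 × ULN or ALT > 2 × ULN) and total bilirubin > 1.5 × ULN, unless Gilbert's]. 'Confirmed' means two consecutive exclusionary results (4.2, opening note). That does not alter the logic.

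| AST or ALT > 2 × ULN | Bilirubin > 1.5 × ULN | As written | Standalone AST/ALT limit | 'or' |
|---|---|---|---|---|
| no | no | admitted | admitted | admitted |
| no | yes | admitted | admitted | excluded (unless Gilbert's) |
| yes | no | **admitted** | excluded | excluded |
| yes | yes | excluded (unless Gilbert's) | excluded | excluded |

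Leaving Gilbert's aside, the rule excludes 1 of 4 combinations, a standalone AST/ALT limit excludes 2, and 'or' excludes 3. The standalone limit removes everyone now removed, plus the isolated AST/ALT elevations.

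**2. Can 'and' be a loose list?** The protocol writes 'or' where one limit is meant to suffice: Exclusions 16d (heart rate, systolic, diastolic), 16e (PR, QTcF) and 18 (FEV₁, FVC). Where Section 10.6.7.1 wants a joint enzyme and bilirubin condition, it writes 'and'. The literal reading is therefore the natural one for a site. The Gilbert's exception is the usual qualifier of a bilirubin limit that stands alone, which suggests 'or' may have been intended. That is an inference; the documents do not say so.

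**3. Is there an AST/ALT limit elsewhere in 4.2?** No. Exclusions 10e and 15 remove some causes of raised enzymes but set no enzyme value. Exclusion 24 sets no value and depends on opinion. The screening review before first dose has no AST/ALT-only limit to apply, and the Day 1 eligibility recheck contains no liver chemistry.

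**4. Illustrative values (chosen here, not taken from the documents).** With bilirubin 1.0 × ULN, confirmed AST/ALT of 2.5, 4, 6 and 9 × ULN all pass Exclusion 20. Against the enzyme-only levels in 10.6.7.1:
- 9 is above 8 × ULN at entry.
- 6 is above 5 × ULN, and could have been so for more than 2 weeks within the 35-day Screening Period.
- 2.5 and 4 are below both levels.

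**5. Set against Section 1.2.** That section names raised enzymes as sufficient for exclusion and mentions no bilirubin condition. All four illustrative subjects fit its description, and Exclusion 20 stops none of them.

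**The case against.** Section 1.2 is narrative and is loose in other places. It says subjects with active infections will be excluded, while Exclusion 11 covers only serious infections needing hospitalization or intravenous treatment. It lists pulmonary disease requiring hospitalization, which becomes a criterion only in the Appendix 11 variant. It also gives no enzyme threshold. This stands, so the truth table describes Exclusion 20 alone. A reader might infer that Section 1.2 and Exclusion 20 differ by exactly one cell, but that would put a 2 × ULN cut into Section 1.2 that is not there. What survives is narrower: a stated precaution that the criteria do not deliver for isolated elevation.

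Section 10.6.7.1 calls itself a basic guide, applies when there is no alternative etiology, and asks only that stopping be considered. An elevation before the first dose cannot be due to study drug. This also stands: those levels illustrate how high the rule lets a subject start, but they are not entry limits.

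A reader might further infer that on-study detection is weaker in such a subject. Appendix 12 does adjust for baseline: for an abnormal baseline of b × ULN, the AST/ALT part of its potential-DILI screen is min(max(2b, 3), 8). That gives 5 × ULN at b = 2.5 and 8 × ULN at b = 4 or 6, against 3 × ULN for a normal baseline; at b = 9 it is already met at entry. But the 10.6.7.1 triggers are fixed multiples of ULN. At a baseline of 4 × ULN, the enzyme part of the trigger pairing > 3 × ULN with bilirubin > 2 × ULN (or INR > 1.5) is already satisfied. Appendix 12's call for closer monitoring above 3 × ULN is also fixed. The documents therefore do not support a general claim of weaker detection.

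Nor do they support inferring an unmonitored gap until the first scheduled post-dose chemistry at Week 4 (Day 29 ± 3). Chemistry is drawn before dosing on Day 1, its results are not among those blinded to sites (Section 6.5), and Investigators must review laboratory reports (Section 10.6.4). The Day 1 result is not required before dosing, however, and none of these provisions sets an entry ceiling.

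**Conclusion.** The point holds. As written, Exclusion 20 excludes one of four combinations of its two limits and leaves isolated AST/ALT elevation of any size to discretion under Exclusion 24. Section 1.2 claims this protection without a bilirubin condition and relies on such precautions for its benefit-risk conclusion. The rule can also admit a subject already above the enzyme-only levels at which 10.6.7.1 says stopping should be considered for suspected drug injury.

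This rests on reading 'and' literally and on the absence of any other AST/ALT limit in Section 4.2. Investigators may well exclude such subjects under Exclusion 24, but sites may differ. The documents give no frequency for isolated elevation, so neither an expected number of such subjects nor a risk can be stated. It is a safety wording fault worth correcting and does not affect the analysis.

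**What to change.** In Exclusion 20, replace 'and' with 'or' so that each limit stands alone: confirmed AST or ALT > 2 × ULN, or total bilirubin > 1.5 × ULN (with the Gilbert's exception kept on the bilirubin limit), at Screening. This preserves the sponsor's bilirubin limit. At minimum, make AST/ALT > 2 × ULN a standalone limit.

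In Section 1.2, replace the general reference to elevated enzymes with that limit and cite Exclusion 20. Mild elevations up to 2 × ULN would still be admitted, so Appendix 12's provision for abnormal baselines keeps its use. Editing Section 1.2 alone would remove the inconsistency but leave no ceiling.

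Cost: an eligibility amendment, with IRB/EC approval and, if substantial, health authority approval (Section 12). A few more screen failures are likely, limited because the value must be confirmed and a failed screening laboratory criterion may be repeated once (Section 4.2). The analysis and sample size do not change.
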